The Effect of Loop Diuretics on Severity and Outcome of Acute Kidney Injury

RESEARCH PLAN

A. Specific Aims

The goal of the study is to determine the severity of acute kidney injury (AKI) early in the clinical course of the disease. Patients who suffer from acute kidney injury can have one of four potential outcomes (1) recovery of kidney function without need for dialysis (2) recovery of kidney function with need for dialysis (3) need for dialysis without renal recovery, and (4) death. The goal of the study is to determine if we can identify which clinical course will occur early in the course of the disease. 5) We seek to determine how well physicians caring for those with AKI can predict the clinical course compared to novel biomarkers of AKI. 6) we seek to determine the association between this clinical course and 3 year patient outcomes.

B. Background and Significance

AKI is a very common disease in patient admitted to the hospital. However, despite advances in supportive care, patients with AKI carry a high mortality rate (50% to 70%).[1] AKI affects nearly 5 percent of all hospitalized persons and as many as 15 percent of critically ill patients. [1, 2] Currently, there are no FDA approved therapeutic agents for the treatment or prevention of AKI.

Recently, at a large international consensus meeting held in Vancouver, BC,[3] the single most important question that was raised by this was the question of when to initiate renal replacement therapy (e.g dialysis). Retrospective studies suggest that the early initiation of renal replacement therapy (RRT) improves outcome. [4-7]

However, a significant subset of patients with AKI recovers without the need for RRT. Many clinicians tend to take a “wait and see” approach because they do not want to dialyze a patient who is destined to recover renal function without the need for RRT. Therefore, it is vitally important to know early in the course which patients with AKI are likely to progress to RRT.

C. Preliminary Studies

The majority of studies on the timing of initiation of dialysis have been case series with historical controls or retrospective case-control series that were performed early after the routine clinical use of dialysis was first introduced. For this reason, the BUN at the initiation of dialysis in the "early" treatment group in these previous studies were high by today's standards.

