retrospective cohort from the Southern AKI Network (SAKI-Net) who were noted to have previously received an FST in the setting of Stage 1 AKI: AUC for AKIN-3 (0.83-0.87) and 0.85-0.89 for AKIN-3 or Death. **Figure 1** demonstrates the UOP in progressors (those reaching Stage 3, n=25) and non-progressors (n=52) in the first 3 hours following FST (n=77). **In our 77 subject cohort, total UOP of less than 200 mls during the first 2 hours post-FST was both a sensitive (87.1%) and specific (84.1%) marker for the progression to Stage 3 AKI.[11]** This cutoff of 200 mls remained extremely sensitive for the composite endpoint of AKIN-3 and death (90%) although the specificity did drop (74.2%). Finally and most importantly, the FST was extremely well tolerated with no episodes of hypotension or any adverse event attributable to the diuretic challenge. This stems from the pre-enrollment selection of patients who were euvoemic and stable for FST as deemed by their treating physicians. Additionally, treating teams were given the option to replace urinary losses after FST with the IV fluid of their choosing.

Table 1: Prospective Cohort - FST ROC-AUCs for Progression to AKIN -3 and Composite Endpoint (n=54)		
	AKIN-3	AKIN-3 or Death
One Hour	0.82(0.07)*	0.74(0.08)*
Two Hour	0.87(0.07)*	0.76(0.08)*
Three Hour	0.87(0.07)*	0.76(0.08)*
Four Hour	0.87(0.07)*	0.76(0.08)*
Five Hour	0.87(0.07)*	0.77(0.08)*
Six Hour	0.86(0.07)*	0.76(0.08)*

*p<0.01

Future studies are needed to validate our preliminary data as well as assess the post-hospital discharge outcomes in this cohort. Once the furosemide challenge is validated and we have a method to identify severe early AKI then and only then can we focus on randomized prospective studies on early versus late RRT in patients with AKI.

D. Research Design and Methods

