We plan to enroll up to 200 patients in a study to determine the feasibility of determining the severity of AKI early in the disease process. Patients with AKI often have tubular injury and therefore renal tubular dysfunction. We hypothesize that patients with severe AKI (AKI that will require RRT) will have more severe tubular dysfunction than patients with less severe AKI (AKI that improves without the need for RRT). Because patients with AKI are often treated with furosemide we plan to test the hypothesis that a poor response to furosemide will identify patients with severe AKI. Furosemide works in the renal tubules, and the ability of furosemide to cause an effective diuresis is contingent on a functioning renal tubule.

Study Design

Patients who are suffering from AKI will be eligible. For purposes of this study, AKI will be defined using the Acute Renal Injury Network(AKIN) criteria[12]: an increase in serum creatinine of greater than or equal to 0.3 mg/dL over 48 hours or increase to greater than or equal to 150 to 200 percent from baseline or sustained oliguria (mean output of <0.5 cc/kg/hr for 6 hours).. For patients who meet entry criteria based on serum creatinine, those subjects must be enrolled within 48 hours of their initial increase in serum creatinine. Patients who have a clinical syndrome consistent with pre-renal or post-renal AKI will be excluded.

Intervention

Once patients are identified and consented, at the time of study entry 7 cc of whole blood and 50 cc of urine will be collected. Thereafter, a single bolus of furosemide will be given to the patient.

Furosemide - If the patient is furosemide naive, they will receive a dose of 1.0 mg/kg. If patient takes a loop diuretic at home, or has been receiving furosemide previous to study entry, the dose of furosemide will be 1.5 mg/kg. The patient will be assessed for 6 hours following the furosemide administration (with a second blood draw/urine collection at 2 hours). All blood draws / urine collections will be 1 tube of blood (5-7 ccs) and 25-50 ccs of urine (when possible)

Baseline urine output and post-furosemide urine output will be recorded. Urinary sediment will also be assessed at both 0 and 2 hours .

Blood Studies - Blood samples (plasma) will be spun down (15 minutes at 1,600 x g) and aliquoted (0.5 ml for plasma) and placed in -80 freezer. These samples will be

assessed for plasma levels of neutrophil gelatinase lipocalin (NGAL) and potentially for other AKI biomarkers.

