- (2) Patients who die before 14d, and whose serum creatinine remains >2.0 mg/dl over baseline creatinine at the time of death
- (3) Patients who die before 14d and whose urine output is less than 400cc/24 hours at the time of death

Renal Recovery

- (1) Patients who do not require RRT and survive 14d or are discharged prior to 14 days
- (2) Patients who die before 14d with a serum creatinine >2.0 mg/dl above their baseline AND with a urine output >400cc/24 hours

Statistical Analysis

Patients will be followed for 30 days or until hospital discharge, whichever occurs first. Need for dialysis, serum creatinine, urine output, medication regimens, and mortality will be assessed. Primary analysis will be based on the net reclassification index as discussed in the sample size section above, additionally we will look at the more traditional receiver operating characteristics (ROC) of urine output and urinary sediment score and biomarkers after furosemide challenge to predict AKI progression. Additionally, time to AKI progression and renal recovery/non-recovery will be assessed. Patient outcomes will be stratified by entry criteria and baseline renal function. We will be looking at the long term, (3 year) outcomes in this cohort as well. However given the focus of this study is to identify severe AKI early in the clinical course and that rates of morbidity and mortality in our ICU- AKI cohort are extremely high, we are not sufficiently powered to look at long term outcomes and this aspect of the study is somewhat exploratory and will serve as pilot data for future studies.

Study Procedures

1. Identify appropriate patients via inclusion/exclusion
2. Consent patient or legal representative
3. Draw 7cc of blood, collect 50cc of fresh urine
4. Bolus dose of furosemide
5. Assess urine output response over the next 6 hours
6. Match urine output with intravenous isotonic saline, 1 ml for 1 ml for 6 hours (at the discretion of the clinically treating team – if they feel diuresis is needed clinically they can decide to hold the intravenous fluids – this has not changed from prior submission)
7. Draw 7cc of blood, collect 50cc of fresh urine 2 hours after the furosemide
8. Draw 7 cc of blood; and another 50cc of urine the following morning at 24 hours post dose
9. Draw 7 cc of blood; and another 50cc of urine at the time of ICU discharge
10. Draw 7 cc of blood; and another 50cc of urine at the time of hospital discharge

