The patient may be exposed to some risks related to blood drawing. We will collect only five (pre-furosemide, 2 hours post-furosemide, 24 hours post-furosemide, ICU discharge and hospital discharge, . Most of the blood samples will be taken by an intravenous catheter which is commonly used in the ICU for treatment purposes. This method of blood drawing will minimize the risks for any possible side-effects. In case the blood is drawn by a needle procedure, there are possibilities of a bruise and slight pain. Rarely, fainting or infection may occur. In addition to blood samples, we will collect two samples of urine samples for all patients in the study. Each urine sample will be 50 milliliter (10 teaspoons of urine over 24 hours). Collection of urine samples does not carry additional risks for the patient because all patients will have an indwelling bladder catheter as part of their study eligibility.

In addition to specimen samples, clinical and laboratory data will be collected from the medical records. . Patients will sign a release of information form at the time of consent that will permit the study team to contact their outside physicians for any / all relevant lab work collected (comprehensive metabolic panel and any urine studies) – this will be done

to allow for determination of post-discharge kidney function to determine if there was any loss of kidney function following the episode of AKI. All data will be held confidential to the investigator in the study. All names and individual identifiers will be separated from the collected data. If and when the data is published, it will be presented in an anonymous fashion to avoid any violation of patient's confidentiality.

Adverse Events

Adverse Events are negative reactions associated with furosemide not present at baseline: hyper-sensitivity reactions (allergic reactions, e.g. rash), dehydration, electrolyte depletion and tinnitus occurring within 24 hours post dose administration. Non-serious AEs will be reported at the time of continuing review.

A study-treatment related adverse event which fits any of the criteria below, is considered a serious adverse event (SAE):

- Results in death
- Is life-threatening (meaning that the patient was at risk of death at the time of the event; this does not refer to an event which might have caused death if it had occurred in a more severe form)
- Requires in-patient hospitalization or prolongs the existing hospitalization

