- Is a persistent disability/incapacity
- Is a congenital anomaly or birth defect
- Is considered an important medical event by the Investigator (e.g., surgery, return to ICU, emergency procedures, etc.)

SAEs will be reported to the IRB within 24 hours of awareness and followed until resolved.

H. Benefits:

There are no direct benefits to the patient in the study. The patient will receive an assessment of renal function that might not otherwise occur but for this study (urine sediment, and renal history and physical assessment). The risks for this study are slightly more than minimal risk.

I. Multi-Institutional Collaboration

The following sites are conducting this study in parallel, with the University of Chicago as the coordinating site:

- George Washington University (PI: [name])
- University of California-San Francisco (PI: [name])

Each site is responsible for study conduct and monitoring independently.

Samples and data from both of all sites will be shared and sent to the University of Chicago. All exchanged samples and data will be de-identified. We will not send or receive data

and/or samples until IRB approval has been granted and subcontracts have been fully executed at respective sites.

J. Outside Consultants/Collaborators (for future research)

Samples of plasma and urine will be stored at UCMC laboratory after initial analysis has been completed per protocol and could be shared in the future with other researchers after they have gained approval by proper authorities to conduct research. These samples will be de-identified prior to sharing for the purposes of future research.

K. Costs To Subjects:

The Section of Nephrology will provide the medicine used in this study free of charge to the patient. The patient will not be charged for anything that is part of the study.

L. Conflicts Of Interest:

There is no conflict of interest.

M. Confidentiality:

In addition to specimen samples, clinical and laboratory data will be collected from the medical records. All data will be held confidential to the investigator in the study. All names and individual identifiers will be separated from the collected data. If and when the data is published, it will be presented in an anonymous fashion to avoid any violation of patient's confidentiality.

N. Subject Compensation:

There is no compensation for being in the study. The medicine and the diagnostic evaluation that are part of the study will be conducted at no charge to the subject.

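### An event becomes an SAE only if it is first deemed related to furosemide, so a zero or low SAE count would bound only the attributed rate

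*Combined protocol and SAP*

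**What the plan says.** Section G (Risks and Side Effects, Adverse Events) sets up two tiers.

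- **AE.** "Adverse Events are negative reactions associated with furosemide not present at baseline". Four types of reaction follow, ending with "electrolyte depletion and tinnitus occurring within 24 hours post dose administration".
- **SAE.** "A study-treatment related adverse event which fits any of the criteria below, is considered a serious adverse event (SAE". The criteria that follow include death, threat to life, prolonged hospitalization and important medical events, with surgery, return to ICU and emergency procedures as examples.

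On reporting, "SAEs will be reported to the IRB within 24 hours of awareness and followed until resolved". Non-serious AEs go to continuing review.

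Under Intervention in section D, "Thereafter, a single bolus of furosemide will be given to the patient"; no untreated or placebo group is described. Section P gives data monitoring to the PI, and section I leaves monitoring to each site. No passage says who judges relatedness or by what rule. The Statistical Analysis text states that "rates of morbidity and mortality in our ICU- AKI cohort are extremely high". For the pilot, section C reports "no episodes of hypotension or any adverse event attributable to the diuretic challenge".

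**The concern.** In the SAE tier, relatedness decides whether an event is counted at all; it is not a property recorded after the event has been logged. That works when the cause of an event is usually clear. Here it usually will not be. The patients are very ill, another explanation is nearly always at hand, every patient had the drug, and sites have no common rule for attribution. The same event two hours after the bolus could be an SAE at one site and unrecorded at another.

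What is at stake is the tolerability statement. The pilot's statement on adverse events was made in terms of attribution, and this larger study is meant to replicate the pilot. With the same condition in its SAE definition it can return another zero without having tested it. The primary reclassification analysis is not affected.

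**Working it through.** **The plan's own figure.** There is none to reproduce. The documents give no expected safety rate, no safety sample size and no stopping boundary.

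**What happens to an event judged unrelated.** Take an event within 24 hours of the bolus that is attributed to the underlying illness.

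- Death, need for dialysis: not an SAE, but collected as an outcome (Statistical Analysis).
- Myocardial infarction, stroke, heart failure: not an SAE, but asked about as part of MARCE at the follow-up contacts (Long Term Follow-up), not as events in a post-bolus window.
- Other non-fatal life-threatening event, return to ICU, emergency procedure: not an SAE, not on the AE list unless it is one of the four reactions, and with no other stated capture beyond general collection from the medical records.

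The gap is the last group.

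**How often a true signal would show as zero.** Inputs:

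- n = 200, the enrolment target (Sample Size).
- p = true rate of serious furosemide reactions. Not in the documents; assumed 1%, 2% and 5%.
- a = probability that a true reaction is attributed to furosemide. Not in the documents; assumed 10% to 100%.

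P(zero counted) = (1 − p·a)^200. For example, p = 0.02 and a = 0.25 give (1 − 0.005)^200 = 0.995^200 = 0.367.

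| a | p = 1% (2 expected) | p = 2% (4 expected) | p = 5% (10 expected) |
|---|---|---|---|
| 10% | 82% | 67% | 37% |
| 25% | 61% | 37% | 8% |
| 50% | 37% | 13% | 0.6% |
| 75% | 22% | 5% | 0.05% |
| 100% | 13% | 1.8% | below 0.01% |

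**What a zero would bound.** With no events in n patients, the exact one-sided 95% upper limit is 1 − 0.05^(1/n). For n = 200 this is 1 − 0.05^(1/200) = 1.49%. It applies to p·a, the attributed rate. The limit on p is 1.49%/a: 2.0% at a = 75%, 3.0% at 50%, 5.9% at 25% and 14.9% at 10%. Because a is unknown and the plan has no way of estimating it, the limit on p is unknown too.

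**What the 100% row does not show.** It counts true drug reactions only. An all-cause SAE count would also include background events, and in this cohort it would seldom be zero even if furosemide did no harm. The 1.8% therefore shows the cost of incomplete attribution. It does not predict what the revised count would be.

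**The case against.** Several points on the other side are sound, and they limit the finding.

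- **The AE tier.** A reader might infer that both tiers depend on a case-by-case judgement. The AE sentence reads naturally as a fixed list with a 24-hour window, so a new rash or electrolyte depletion would count without one. The point rests on the SAE tier.
- **Lost data.** A reader might infer that excluded events can never be looked at again. The documents do not support that: clinical and laboratory data are taken from the medical records, and death, dialysis and MARCE are collected whatever the cause. What is missing is a prompt, dated safety record, so later review would mean retrospective chart work.
- **Who judges.** It is tempting to say that the investigators running the test grade their own intervention. No passage says so. The investigator is named only for the important-medical-event criterion. The supportable statement is that no assessor is named.
- **The pilot.** The qualifier about attribution may apply only to adverse events in general, so the hypotension statement may have been unfiltered.
- **No safety analysis is planned.** Safety is not among the aims, and the SAE definition's stated use is IRB reporting. This limits the consequence to the AE/SAE counts and any tolerability statement built on them. Since the pilot made such a statement prominently, another is likely.
- **Overlap with the closed AE list.** If an SAE must first be a listed AE, unlisted events are already excluded before relatedness is considered. The revised definition therefore has to override the list as well.
- **No control group.** All-cause counts cannot by themselves separate drug harm from background illness. This stands. Their value is that others can review them and, where a background rate exists, compare them with it.

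**Conclusion.** The concern holds for the SAE tier. Relatedness is a condition for being counted, the plan gives no assessor, causality rule or comparator, and non-fatal serious events put down to the underlying illness enter no AE or SAE count. A zero or low SAE count would bound the attributed rate only.

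The size depends on two figures that the documents do not give. At an assumed 2% true reaction rate, the chance of counting none in 200 patients runs from 67% at 10% attribution through 37%, 13% and 5% to 1.8% at full attribution. The direction is the same for any attribution below 100%; the amount is illustrative. The absence of a control group and of blinding is inferred from the design as described.

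A reader might go further and conclude that the study would hide major harm or that its results would be invalid. The documents do not support this: deaths, dialysis and MARCE are recorded regardless of cause, and the primary analysis does not use the AE or SAE counts. The change is still worth making, because it is cheap and makes the tolerability count reviewable.

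**What to change.** In the Adverse Events text of section G:

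1. Define an SAE as any event that meets the existing seriousness criteria with onset within 24 hours of the bolus, regardless of cause and whether or not it is on the AE list.
2. Record relatedness to furosemide as a separate field, and state who assesses it and on what criteria, the same at all sites.
3. Report all-cause and related counts side by side.
4. Reword the expedited IRB sentence to cover related SAEs only, so that current reporting does not change. The present SAE sentence has no time window of its own, so keep any related event with later onset reportable as well.

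**Cost.** Protocol wording and one field on the form. More events are logged, but only over 24 hours in 200 patients, who are already assessed for 6 hours and sampled at 24 hours. The safety table will look less favourable, and the report should say that without a control group the all-cause count does not by itself measure drug harm. Eligibility, endpoints and sample size are unchanged.
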